## 6. EFFICACY ANALYSES

Imaging-based tumor assessments will be performed within 28 days prior to the start of treatment. On-study tumor assessments will be performed at ~8- to 12-week intervals at visits 1, 6, 9, 11, 13, and 15 (corresponding to baseline, Weeks 8, 16, 24, 36, and 48) and every 12 weeks thereafter. An end-of-treatment tumor assessment (if the subject withdraws from the study for reasons other than tumor progression on a routine imaging/scan) should be performed if the last assessment was performed > 4 weeks prior to end-of-treatment visit.

Imaging-based tumor assessments include site of lesion and bi-dimensional measures for the largest diameter and the perpendicular diameter. Tumor response will be evaluated by both investigators and IRC.

Data will be presented for both investigators assessments and IRC assessments. A subject's response status at each visit, best overall response (BOR), date of progression and date of first response will be determined by IRC and recorded in the IRC database. The findings of IRC will be considered primary for analyses of ORR and other tumor control endpoints (ie, DOR, TTR, % changes in tumor size and PFS). Consistency of evaluation between IRC and investigator assessments will be summarized by the percent agreement for overall response.

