### **6.4. Secondary Efficacy Endpoints**

#### **6.4.1. Definition of Secondary Efficacy Endpoints**

- DOR – defined as the interval from the first documentation of CR or PR (or MR for WM subjects) to the earlier of the first documentation of disease progression or death from any cause
- LNR – defined as the proportion of subjects who achieve a  $\geq 50\%$  decrease from baseline in the SPD
- TTR – defined as the interval from the start of study drug to the first documentation of CR or PR (or MR for WM subjects)
- PFS – defined as the interval from the start of study drug to the earlier of the first documentation of disease progression or death from any cause
- OS - defined as the interval from the date of first IDELA to death from any cause
- Changes in HRQL as reported by subjects using the FACT-Lym
- Changes in performance status as documented using the Karnofsky performance criteria

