#### **6.4.2. Analysis Methods for Secondary Efficacy Endpoints**

##### **6.4.2.1. Duration of Response and Progression-Free Survival**

The date of definitive progression will be the timepoint at which progression is first identified by relevant radiographic or imaging data. Death occurring  $\leq$  30 days following the discontinuation of study drug will be considered as an event for the DOR and PFS calculation. Data will be censored on the date of the last tumor assessment (including assessments with a NE outcome) for subjects

- who do not have disease progression or die within 30 days after discontinuation of the study drug, or
- who start new anti-tumor therapy prior to documented disease progression, or
- who have 2 or more consecutive missing tumor assessments before disease progression or death.

Subjects without adequate baseline tumor response evaluation will be censored on Study Day 1. PFS will also be summarized for responding subjects (ie, subjects with a CR or PR) and non-responding subjects separately.

To assess the robustness of the primary DOR and PFS results, the following sensitivity analyses will be performed:

- DOR and PFS will be assessed based on IRC assessments using the PP analysis set based on the same censoring rules as above.
- DOR and PFS will be assessed based on investigators assessments using the same censoring rules as above.
- DOR and PFS will be assessed based on the first PD identified by IRC without consideration of any drug interruption or the response status post that PD with all other censoring rules staying the same as the primary analysis.

PPD

DOR and PFS will be summarized using KM methods and KM curves for DOR and PFS will be provided. All the derived endpoints will be listed.

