### **7.1.6. Summaries of Adverse Events and Deaths**

A brief summary of treatment-emergent AEs will show the number and percentage of subjects who (1) had any AE, (2) had any Grade  $\geq 3$  AE, (3) had any treatment-related AE, (4) had any Grade  $\geq 3$  treatment-related AE, (5) had any SAE, (6) had any treatment-related SAE, (7) discontinued from study drug due to an AE, (8) dose reduction due to an AE, (9) death due to AEs (10) death during study drug treatment up to 30 days post last dose and (11) all deaths including long-term follow up .

Summaries (number and percentage of subjects) of treatment-emergent AEs (by SOC, HLT and PT) will be provided as follows:

- All AEs
- All AEs by severity
- Grade  $\geq 3$  AE
- All AEs occurring in at least 10% of subjects
- All treatment-related AEs
- All treatment-related AEs by severity
- Grade  $\geq 3$  treatment-related AEs
- All SAEs
- All treatment-related SAEs
- All AEs that caused discontinuation from study drug
- AEs leading to deaths

Multiple events will be counted once only per subject in each summary. For data presentation, SOC, HLT and PT will be sorted by decreasing frequency. For summaries by severity grade, the most severe event will be selected. In addition to the presentation by SOC and HLT, each summary listed above will also be presented by preferred term in decreasing frequency.

Summary of all treatment-emergent AEs will also be summarized by SOC, HLT and PT, and by PT only in the following subgroups: sex (Male or Female), age group ( $<65$  or  $\geq 65$  years) and race (White or Non-White).

In addition to the by-treatment summaries, data listings will be provided for the following:

- All AEs (with a variable indicating whether the event is treatment-emergent)

- SAEs (with a variable indicating whether the event is treatment-emergent)
- AEs leading to deaths
- AEs leading to discontinuation of study drug

Relative day from first dose date will be provided for each AE in the listings. If the AE onset date is after the first dose date, the relative day will be calculated as (AE onset date – first dose date + 1), however, if the AE onset date is prior to the first dose date, the relative day will be calculated as (AE onset date- first dose date).

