2.4.2.4	Duration of Response - Investigator Assessments - by Disease	ITT Analysis Set
2.4.2.5	Duration of Response - Investigator Assessments - by Number of Prior Therapies	ITT Analysis Set
2.4.2.6	Duration of Response - Investigator Assessments - by Refractory to Last Prior Therapy	ITT Analysis Set
2.4.2.7	Duration of Response - Investigator Assessments - by Longest Diameter of Baseline Lesion	ITT Analysis Set
2.4.2.8	Duration of Response - Investigator Assessments - by Prior Use of Bendamustine	ITT Analysis Set
2.4.2.9	Duration of Response - Investigator Assessments - by Refractory to Bendamustine	ITT Analysis Set
2.4.2.10	Duration of Response - Investigator Assessments - by Number of Times Refractory to an Alkylating Agent	ITT Analysis Set
2.4.2.11	Duration of Response - Investigator Assessments - by Number of Times Refractory to Rituximab	ITT Analysis Set
2.4.2.12	Duration of Response – Investigator Assessments – by Suitability for Radioimmunotherapy	ITT Analysis Set
2.4.2.13	Duration of Response – Investigator Assessments – by Region	ITT Analysis Set
2.4.3	Duration of Response - Independent Review Committee (IRC) Assessments	Per Protocol Analysis Set
2.4.4	Duration of Response - Investigator Assessments	Per Protocol Analysis Set
2.4.5	Duration of Response – Investigator Assessments (Sensitivity Analysis)	ITT Analysis Set
2.5.1	Progression Free Survival - Independent Review Committee (IRC) Assessments	ITT Analysis Set
2.5.1.1	Progression Free Survival - Independent Review Committee (IRC) Assessments - by Gender	ITT Analysis Set
2.5.1.2	Progression Free Survival - Independent Review Committee (IRC) Assessments - by Age	ITT Analysis Set
2.5.1.3	Progression Free Survival - Independent Review Committee (IRC) Assessments - by Race	ITT Analysis Set
2.5.1.4	Progression Free Survival - Independent Review Committee (IRC) Assessments - by Disease	ITT Analysis Set

Table Number	Title	Analysis Set
2.5.1.5	Progression Free Survival - Independent Review Committee (IRC) Assessments - by Number of Prior Therapies	ITT Analysis Set
2.5.1.6	Progression Free Survival - Independent Review Committee (IRC) Assessments - by Refractory to Last Prior Therapy	ITT Analysis Set
2.5.1.7	Progression Free Survival - Independent Review Committee (IRC) Assessments - by Longest Diameter of Baseline Lesion	ITT Analysis Set
2.5.1.8	Progression Free Survival - Independent Review Committee (IRC) Assessments - by Prior Use of Bendamustine	ITT Analysis Set

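### SAP Section 6.4.2.1 censors progression-free deaths more than 30 days after stopping drug, although Section 6.4.1 counts every death as a PFS and DOR event

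*SAP*

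**What the plan says.** Section 6.4.1 runs DOR from first response, and PFS from the start of study drug, in both cases "to the earlier of the first documentation of disease progression or death from any cause". It sets no time limit on the death. Section 3.1.2 also describes a PFS event as PD or death, without a limit.

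Section 6.4.2.1 then gives the rule for the analysis. A death no later than "30 days following the discontinuation of study drug will be considered as an event for the DOR and PFS calculation". Censoring is at the last tumor assessment for three groups:

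- subjects "who do not have disease progression or die within 30 days after discontinuation of the study drug, or"
- subjects who start new anti-tumor therapy before documented progression
- subjects "who have 2 or more consecutive missing tumor assessments before disease progression or death"

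Three sensitivity analyses are visible. The first two (per-protocol set, investigator assessments) use the same censoring rules. The third changes which PD is taken, "with all other censoring rules staying the same as the primary analysis". A redacted block follows. Section 13 also lists Tables 2.4.5 and 2.5.5 as investigator-based sensitivity analyses, whose content the visible text does not define.

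Section 1.2 has follow-up running from the last dose up to Year 5. Section 7.1.6 tabulates "all deaths including long-term follow up", and Table 2.8.2 uses those deaths for OS.

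**The concern.** The definition and the analysis rule disagree on which deaths are events. The disagreement is in the main analysis of two endpoints that, in a single-arm trial, help the reader interpret the response rate. The deaths in question are collected and used elsewhere in the SAP, so lack of data does not explain leaving them out. Censoring at the last scan is also uninformative only if subjects who stop drug without progression carry the same later risk as those who stay on it. In the visible text no sensitivity analysis tests the 30-day limit.

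**Working it through.** **Can another censoring rule explain the exclusion?** Take a subject who stops drug at Week 20, has an end-of-treatment scan without PD, starts no new therapy and dies 45 days later.

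- Death falls at 20 + 45/7 = Week 26.4.
- Scans are due at Weeks 8, 16 and 24, then every 12 weeks. Only Week 24 has passed, so at most one assessment is missing and the two-missed rule does not apply.
- The new-therapy rule does not apply.
- Section 6.4.1 makes the death an event. Only the 30-day limit removes it.

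The next scan is due at Week 36, which is 36 − 20 = 16 weeks after stopping. For this subject any death from day 31 to about day 112 (16 × 7) is excluded by the 30-day limit alone.

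**Size.** The SAP states no event count, median or rate for PFS or DOR, so there is no figure to reproduce and every rate below is an assumption. Simulation, 400,000 subjects per setting:

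- From the SAP: accrual over 15 months, cut-off 24 weeks after last entry, the scan schedule, and an end-of-treatment scan if the last one was more than 4 weeks earlier.
- Assumed: no scans after that one; median time to PD 7, 11 or 18 months; stopping without PD at 0.01 or 0.03 per month; death on drug at 0.005 per month; seven off-drug death patterns (0.005, 0.02 or 0.05 constant; 0.10 for 30 days then 0.02; 0.20 for 30 days then 0.005, 0.02 or 0.05); new therapy at 0 or 0.1 per month. That is 3 × 2 × 7 × 2 = 84 settings.
- DOR: a random 55% of subjects on drug, alive and without PD at Week 8, timed from that scan.

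Deaths dropped by the 30-day limit: 0.1 to 8.4 per 125 subjects. If scan dates after the end-of-treatment scan count as missed, an any-death rule that keeps the two-missed rule brings back 0.1 to 3.0 of them.

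Differences at 12 months, in percentage points:

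| Comparison | PFS | DOR |
|---|---|---|
| SAP rule minus any-death rule, post-treatment dates counted as missed | 0.0 to +2.2 | 0.0 to +2.4 |
| SAP rule minus any-death rule, those dates not counted | +0.1 to +4.5 | +0.1 to +4.5 |
| SAP rule minus complete follow-up | −1.8 to +2.5 | −2.0 to +2.1 |
| Any-death rule with two-missed rule minus complete follow-up | −1.9 to +0.7 | −2.2 to +0.2 |

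Three settings with median time to PD 11 months, 12-month PFS:

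| Assumed rates per month | Complete follow-up | SAP rule | Any death, two-missed rule | Any death, no two-missed rule |
|---|---|---|---|---|
| Stop 0.01, death 0.005 on and off drug | 0.470 | 0.465 | 0.464 | 0.464 |
| Stop 0.03, off-drug death 0.05 | 0.436 | 0.452 | 0.436 | 0.420 |
| Stop 0.03, off-drug death 0.20 for 30 days then 0.005 | 0.447 | 0.431 | 0.429 | 0.428 |

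An independent run of these three settings agreed within about 0.4 points.

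Two effects pull in opposite directions. Dropping later off-drug deaths raises the curve. Counting deaths in the first 30 days, while survivors of that window are censored back at their last scan, lowers it.

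A second simulation used heavier assumed rates (median time to stopping without PD 12 or 24 months, median survival after stopping 6 to 24 months) and no two-missed or new-therapy rule. It dropped about 5 to 22 deaths per 125 and put 12-month PFS about 1 to 6 points above the any-death rule.

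For scale, the 95% half-width for a proportion near one half with 125 subjects is 1.96 × √(0.5 × 0.5/125) = 0.088, about 9 points. It is wider for DOR, which uses responders only.

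**The case against.** The new-therapy and two-missed rules also censor deaths that Section 6.4.1 would count, so the proposed rule does not restore the definition in full: at most 3.0 of up to 8.4 dropped deaths return if post-treatment dates count as missed. This stands. It is why the counting of those dates has to be stated. The difference is that those two rules respond to a loss of information about progression, whereas the 30-day limit removes a known death even when neither applies.

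The statistical gain is modest. In two of the three settings shown the any-death rule is 0.1 to 0.2 points further from complete follow-up than the SAP rule. That also stands. A reader might infer that the SAP rule systematically flatters PFS and DOR, and the calculations do not support this. The upward bias appears mainly where off-drug mortality stays high.

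A reader might also infer that no any-death analysis is planned. The redacted block and the undefined Tables 2.4.5 and 2.5.5 rule out that conclusion. The contradiction in the main analysis remains either way.

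Amending Section 6.4.1 to match the rule would remove the contradiction at less cost, but known deaths would still be left out.

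Whether scans continue after treatment is a protocol matter. Their absence is an assumption here, based on a schedule table that did not extract cleanly.

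Finally, Section 6.4.2.4 gives no explicit censoring date in the on-study OS analysis (Table 2.8.1) for a subject who dies after the 30-day window. A sound reading is available and any-death OS is specified, so this is a clarification only.

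**Conclusion.** The contradiction between Sections 6.4.1 and 6.4.2.1 is real, and no other censoring rule accounts for it. As written, the main PFS and DOR analyses do not estimate the defined endpoints, and they discard deaths the study already records.

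The effect is probably small. Over the 84 assumed settings it is 0 to about 2.4 points at 12 months against an any-death rule that keeps the two-missed rule, and up to about 4.5 points if post-treatment dates are not counted as missed. Even the heavier assumptions, at about 6 points, stay inside the half-width of about 9. None of these rates comes from the SAP, and the direction of bias against complete follow-up is not fixed.

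The reasons to change the rule are agreement with the definition, use of known deaths, and removal of the upward bias when off-drug mortality is high. Both endpoints are descriptive secondaries and ORR is untouched, so this is worth correcting but does not threaten the primary result.

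**What to change.** In Section 6.4.2.1:

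- Count any death before new anti-tumor therapy as a PFS and DOR event, subject to the existing two-missed-assessments rule.
- State whether scheduled scan dates after the end-of-treatment scan count as missed, because this decides how many deaths return.
- Keep the 30-day version as a sensitivity analysis.

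If the redacted text already holds an any-death analysis, exchange its place with the 30-day one.

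The cost is SAP wording and minor reprogramming; the death dates are already needed for Section 7.1.6 and Table 2.8.2. The PFS and DOR estimates may become slightly less favourable. Because 125 subjects are already enrolled in an open-label study, record the change and its reason in the SAP revision table (Section 12).

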### **3. GENERAL CONSIDERATIONS FOR DATA ANALYSES**

#### **3.1. Analysis Sets**

##### **3.1.1. Intent-to-Treat Analysis Set**

The intent-to-treat (ITT) analysis set will comprise all subjects who receive  $\geq 1$  dose of IDELA. The ITT analysis set will be used in the analyses of ORR, progression-free survival (PFS), overall survival (OS), safety, and study drug administration and compliance. The ITT analysis set will be the primary analysis set for all the efficacy variables.

Duration of response (DOR) and time-to-response (TTR) will be analyzed based on all ITT subjects who achieve a CR or PR (including MR for subjects with WM). Lymph node response rate (LNR) will be analyzed based on all ITT subjects who have both baseline and  $\geq 1$  evaluable post-baseline tumor assessments.

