### 6.1. Definition of the Primary Efficacy Endpoint

A best overall response of CR, PR, stable disease (SD), PD, not evaluable (NE) and no disease (ND) is allowed. For subjects with WM, a minor response (MR) is also allowed. In the event that a single PD is followed by an assessment that is SD, PR or CR which is the same or better than the prior nadir response and there is substantial interruption of exposure to study drug, that PD may not be considered in the BOR evaluation in accordance with the Gilead Protocol 101-09 Imaging Charter.

ORR is defined as the proportion of subjects who achieve a CR or PR (or MR for subjects with WM) during the IDELA treatment. The response definitions for each category are based on standard criteria and defined in Section 8.1.5 of the protocol. Subjects who do not have sufficient baseline or on-study tumor status information to be adequately assessed for response status (ie, those with best overall responses of NE or ND) will be included in the denominators in calculations of response rates.

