### **6.3. Analysis of the Primary Efficacy Endpoint**

The ORR and 95% CI will be presented along with the corresponding p-value from the exact binomial test. The number and proportion of subjects who were evaluated as CR, PR, SD, PD, NE, and ND will also be tabulated.

The primary analysis for ORR will be conducted in the ITT set based on the IRC assessments. The investigator assessments will also be summarized. Both investigator and IRC assessments for tumor response will be listed in detail including site of lesion, date and method of evaluation, bidirectional measures and sum of the products of the perpendicular diameters of measurable index lesions (SPD). Summaries will also be provided for response at each visit separately when tumor assessment is available.

Agreement in best overall response between IRC and investigator assessments will be summarized.

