#### 6.4.2.3. Time to Response

TTR will be evaluated using both the IRC and investigators data based on ITT and PP subjects who achieve a CR or PR (or MR for WM subjects). TTR will be summarized using descriptive statistics.

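### The PFS summary by responder status runs from first dose, which favours responders by construction, and its responder definition omits MR for WM

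*SAP*

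**What the plan says.** Section 6.4.2.1 of the SAP, after the censoring rules for DOR and PFS, adds that "PFS will also be summarized for responding subjects (ie, subjects with a CR or PR) and non-responding subjects separately". DOR and PFS are to be summarised by Kaplan-Meier methods. The visible text gives no landmark, no time-dependent treatment of response and no caveat on how to read the split.

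The PFS clock is fixed in Section 6.4.1: "PFS – defined as the interval from the start of study drug". Section 3.8.1 makes the day of first dose Study Day 1. Section 6 places the tumour assessments "at visits 1, 6, 9, 11, 13, and 15 (corresponding to baseline, Weeks 8, 16, 24, 36, and 48"), so Week 8 is the first scheduled scan that can show a response.

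On who counts as a responder, other sections differ from Section 6.4.2.1:
- Section 3.1.1 analyses DOR and TTR "based on all ITT subjects who achieve a CR or PR (including MR for subjects with WM").
- Section 6.1 says "For subjects with WM, a minor response (MR) is also allowed" as a best overall response, and counts it in ORR.
- Section 6.4.1 includes MR for WM in the definitions of DOR and TTR.
- Section 6.4.2.3 evaluates TTR "based on ITT and PP subjects who achieve a CR or PR (or MR for WM subjects").

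For the primary endpoint, Section 6.3 plans this breakdown: "The number and proportion of subjects who were evaluated as CR, PR, SD, PD, NE, and ND will also be tabulated". MR is not among the categories.

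**The concern.** The two groups are formed by something that happens after the clock starts. To be called a responder, a subject must have stayed progression-free until the scan that showed the response. Subjects who progress or die before then can only be non-responders. This is guarantee-time (immortal-time) bias. It pushes the two Kaplan-Meier curves apart whether or not response is related to later progression, and a reader cannot tell how much of the gap is real. In a single-arm trial, side-by-side responder and non-responder curves are easily read as evidence that response prolongs PFS.

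The definition adds a second problem. A WM subject whose best response is MR would be a responder for ORR, DOR and TTR but a non-responder for this PFS split. If any such subject exists, the CR and PR rows of the Section 6.3 table will not add up to the primary ORR numerator.

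**Working it through.** **No figure to reproduce.** The SAP attaches no number to this split. The direction of the bias follows from the definitions. Its size needs assumptions, which are stated here.

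**Inputs from the SAP.** PFS runs from first dose (6.4.1). Scans are at Weeks 8, 16, 24, 36 and 48 (Section 6). The alternative for ORR is 39% (1.3).

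**Assumptions not in the SAP.** Response is independent of PFS. PFS is exponential with a true median of 8, 11 or 14 months. A proportion p of subjects (40% to 60%) would respond if they stayed event-free long enough. Their responses would first be seen 60/25/15% at Weeks 8/16/24, varied to 80/15/5% and 40/35/25%. There is no censoring.

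**Formulas.** With S(t) = exp(−ln 2 × t/median), the Week 48 scan is the last before 12 months, so 12-month PFS is S(48).
- Chance that a would-be responder is still event-free at the response scan: q = 0.60·S(8) + 0.25·S(16) + 0.15·S(24)
- Observed ORR: p·q
- Apparent 12-month PFS in responders: S(48)/q
- Apparent 12-month PFS in non-responders: (1 − p)·S(48)/(1 − p·q)

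**Median 11 months (47.83 weeks).** S(8) = 0.8905, S(16) = 0.7931, S(24) = 0.7062 and S(48) = 0.4988.

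q = 0.60 × 0.8905 + 0.25 × 0.7931 + 0.15 × 0.7062 = 0.8385.

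Responders: 0.4988/0.8385 = 59.5%.

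Non-responders at p = 0.465, where the observed ORR is 0.465 × 0.8385 = 39.0%: 0.535 × 0.4988/(1 − 0.3899) = 43.7%.

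| True median | True 12-month PFS | p | Responders | Non-responders | Gap (points) |
|---|---|---|---|---|---|
| 8 months | 38.4% | 0.40 | 48.9% | 33.6% | 15.2 |
| 8 months | 38.4% | 0.60 | 48.9% | 29.1% | 19.8 |
| 11 months | 49.9% | 0.40 | 59.5% | 45.0% | 14.5 |
| 11 months | 49.9% | 0.465 | 59.5% | 43.7% | 15.7 |
| 11 months | 49.9% | 0.60 | 59.5% | 40.15% | 19.3 |
| 14 months | 57.9% | 0.40 | 66.5% | 53.3% | 13.2 |
| 14 months | 57.9% | 0.60 | 66.5% | 48.5% | 18.1 |

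Gaps are taken before rounding. With the earlier and later response timings added, the gap runs from 10.7 to 23.2 points. The true gap is zero in every case.

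**Landmark at Week 16.** Among subjects event-free at Week 16, 12-month PFS is S(48)/S(16) in both groups: 52.9%, 62.9% and 69.5% for medians of 8, 11 and 14 months. The artefact disappears.

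**Second check, with other assumptions.** A simulation of 200,000 subjects per scenario used true medians of 26, 39 and 52 weeks, response unrelated to PFS, and latent responses in 20/10/10% or 35/10/5% of subjects at Weeks 8/16/24. Counted from Day 1:
- At a true median of 39 weeks, median PFS was 49.8–52.9 weeks in responders against 29.7–31.4 in non-responders.
- Across all scenarios, the apparent event-rate ratio was 0.64–0.77, where the truth is 1.0.
- Week 8 PFS was 100% in responders and 69–85% in non-responders.

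With a Week 24 landmark, median remaining PFS at the 39-week setting was 38.8–39.1 against 39.1–39.2 weeks.

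**The definition.** This needs no arithmetic. Sections 3.1.1, 6.1, 6.4.1 and 6.4.2.3 count MR for WM as a response, and Section 6.4.2.1 does not. LPL/WM is an eligible subtype (Section 1.2), so the case can arise.

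**The case against.** The strongest reply is that this is one sentence about a descriptive summary. No test, hazard ratio or claim about response is attached. Section 13 lists no PFS table by responder status, although it lists 13 PFS subgroup tables for each type of assessor. That stands, and it limits the reach of the point. It does not remove the problem, because Section 6.4.2.1 still commits to the summary and its only natural use is the biased comparison.

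DOR starts at the first documented response and so gives responders' later course without guaranteed time. True, but it offers no comparison with non-responders. There is also redacted text in Section 6.4.2.1. Nothing is inferred from it.

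A progression may be disregarded in the best-response evaluation when drug was substantially interrupted. A subject could then be a responder after an event, but only in the sensitivity analysis that counts that first progression.

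The size depends on inputs the SAP does not give, and the model leaves out the censoring rules. That stands: the 11 to 23 points illustrate the size and do not predict it for this trial. The direction does not depend on those inputs.

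A Week 16 landmark drops subjects and misplaces late responders, and a one-line caveat would be cheaper. A caveat would warn the reader but leave the biased curves in the report. A subject whose last scan falls just before Day 116 would be censored and excluded, but would contribute no time after the landmark anyway.

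Finally, the CR or PR wording may be shorthand, and the number of MR subjects may be zero. Both are possible, but the text as written conflicts with four other sections.

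**Conclusion.** Both parts hold. Counting PFS from first dose while grouping on later response favours responders by construction. If response has no bearing on PFS, the apparent 12-month difference is 11 to 23 points for true medians of 8 to 14 months, response propensities of 40–60% and the three response timings. It is about 16 points at the SAP's alternative ORR of 39% with an 11-month median. These figures rest on exponential PFS and no censoring. If response is in fact related to PFS, part of the observed gap would be real, and the planned summary could not show how much.

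The responder definition contradicts the one used for ORR, DOR and TTR, and the Section 6.3 categories omit a best response that Section 6.1 allows. How many subjects this affects is unknown. The point should be corrected, but it does not affect the primary ORR test or the overall ITT PFS.

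**What to change.** - In Section 6.4.2.1, replace the responder split with a landmark Kaplan-Meier summary at one pre-specified scan, for example Week 16. Set the landmark at Study Day 116, which is Day 113 plus the 3-day visit window in the Schedule of Assessments. Include only subjects event-free and still under follow-up on that day, group them by IRC response up to that day, and count PFS from that day.
- Define a responder there as CR, PR, or MR for WM subjects.
- Add an MR row to the Section 6.3 tabulation, so that its response rows sum to the ORR numerator.
- Add the landmark table to the Section 13 list.

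**Cost.** SAP wording, one table and one added row. Under the assumptions above, 17–27% of subjects (1 − S(16), for medians of 14 to 8 months) have an event by Week 16 and leave this supportive summary. About 8–17% of its non-responders respond later at the base timing, and 3–25% over the timing range. Overall ITT PFS still covers everyone.
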